PROTOCOL

(Version April 2015)

TRIGR

Trial to Reduce IDDM in the Genetically at Risk

RESEARCH DESIGN AND METHODS

This is a randomized double blinded intervention study using an intention to treat statistical analysis to compare the incidence of predictive autoantibodies and clinical diabetes in the two treatment groups.

A. STUDY POPULATION

Newborn infants who have a first degree relative (FDR) with type 1 diabetes (i.e. a mother, father or full sibling), and who meet the inclusion but not the exclusion criteria are recruited:

Inclusion criteria:

1. The biological parent and/or full (not half) sibling of the newborn infant has type 1 diabetes as defined by the World Health Organization
2. The infant's parent or legal guardians give signed consent to participate

Exclusion criteria:

1. An older sibling of the newborn infant has been included in the TRIGR intervention
2. Multiple gestation
3. The parents are unwilling or unable to feed the infant cow's milk (CM) based products for any reason (e.g., religious, cultural).
4. The newborn infant has a recognizable severe illness such as those due to chromosomal abnormality, congenital malformation, respiratory failure needing assisted ventilation, enzyme deficiencies, etc.
5. The gestational age of the newborn infant is less than 35 weeks
6. Inability of the family to take part in the study (e.g. the family has no access to any of the Study Centers, the family has no telephone)
7. The infant has received any infant formula other than Nutramigen prior to randomization
8. The infant is older than 7 days at randomization
9. No HLA sample drawn before the age of 8 days

B. SAMPLE SIZE

The sample size estimation presented in Table 1 is based on experiences from family studies analyzing the occurrence of autoantibodies in siblings of children with type 1 diabetes or in offspring of affected parents and progression to clinical disease in such young first-degree relatives. The data on the frequency of multiple (≥ 2) autoantibodies by the age of 6 years and the cumulative incidence of type 1 diabetes by the age of 10 years are based on 82 young siblings from the DiMe Study carrying increased genetic risk for type 1 diabetes as defined according to the criteria in the Pilot-2 trial (106).

Nineteen out of 325 offspring (5.9%) with increased genetic risk according to the criteria used in the Pilot-2 trial tested positive for at least one autoantibody by the age of 2.4 years in the German BABYDIAB study (107). Seventeen of these 19 subjects (89%) developed multiple autoantibodies during prospective observation. Assuming a constant increase in autoantibody frequency from age 2 to

age 6 years, the expected cumulative incidence of at least one antibody would be 14.8% and that of at least two antibodies 13.0% by the age of 6, which is well within the 95% CI of the observed frequency of 20.7% of multiple autoantibodies in the young DiMe siblings.

The cumulative incidence of at least one autoantibody by the age of 4 years was 10.6% in siblings and offspring of affected subjects in the DAISY study from Denver (108). The frequency reached 37.9% in those carrying the DR3/4, DQB1*0302 combination. Published data are not available allowing an estimation of the frequency of at least one or at least two autoantibodies in subjects with increased genetic risk as defined in the Pilot-2 trial. Nevertheless a constant increase in the frequency of at least one autoantibody from age 4 to age 6 years, would result in an autoantibody prevalence of 15.9% by the age of 6 years in siblings and offspring irrespective of HLA-defined genetic risk. The DiMe study was used for the power calculation as it includes the largest long term follow-up of young relatives.

The estimation that 2032 infants should be randomized for the trial (Table 1) is based on the following assumptions:

1. a confidence level of 95%;
2. a statistical power of 80%;
3. a reduction of 40% in the hazard rate of type 1 diabetes in the intervention group;
4. a drop-out rate of 20%; and
5. a frequency of 10% of exclusive breast feeding (BF) up to the age of 6 months

These figures represent a conservative estimate, since they are based on the lower 95% CI (7.6%) of the observed cumulative incidence of type 1 diabetes by the age of 10 years (15.4%) in young siblings with moderate (DQB1*0302/x) and slightly increased genetic risk (DQB1*02/y), and since the high risk (DQB1*02/0302) group was not considered in the calculations. In the Pilot-2 trial the prevalence of the high risk genotype (DQB1*02/0302) was about two times higher (absolute frequency 20%) among siblings of affected children than among offspring of affected parents. If also the young siblings carrying the high risk genotype in the DiMe Study should be included in the group at risk, the lower 95% CI would be 10.6%, which should result in a recommendation of 1920 infants to be randomized for the trial. However, fewer data from non-Finnish populations are available, explaining the caution of this sample size estimate.

Table 1. Estimation of the sample size for the trial

Assumptions:									
• Confidence level:	95%								
• Power:	80%								
• Reduction in the annual frequency of multiple auto-antibodies (≥ 2 AB) by the age of 6 years	30, 40 or 50%								
• Reduction in the annual frequency of type 1 diabetes by the age of 10 years	30, 40 or 50%								

Frequency of ≥ 2 AB by the age of 6	SAMPLE SIZE								
	30% effect			40% effect			50% effect		
	I	II	III	I	II	III	I	II	III
20.7% (*02 and/or *0302)	1048	1132	1165	558	602	626	338	364	382
18.5% (*0302/x, *02/y)	1196	1294	1330	636	688	716	386	418	438
9.9% (lower 95% CI)	2252	2438	2511	1200	1300	1334	732	792	832

Frequency of type 1 diabetes by the age of 10	SAMPLE SIZE								
	30% effect			40% effect			50% effect		
	I	II	III	I	II	III	I	II	III
18.3% (*02 and/or *0302)	1330	1492	1536	706	794	824	428	482	502
15.4% (*0302/x, *02/y)	1548	1782	1834	844	948	986	512	576	606
7.6% (lower 95% CI)	3250	3658	3768	1735	1952	2032	1056	1190	1250

Column I: Mathematical sample size
Column II: Sample size corrected for a drop-out rate of 20%
Column III: Sample size corrected in addition for a 10% frequency of exclusive BF up to the age of 6 months.

RECOMMENDATION: 2032 infants and families
SCREENING TARGET: 4516 infants

[figure not shown]
All statistical analyses will be based upon the total cohort of subjects randomized into the trial. Although data on some subjects may be missing at points in time, all relevant data available from each subject will be employed in the analyses. In all principal analyses, subjects will be included in the group

to which they were initially assigned and this assignment will not be altered based on a subject's adherence to the assigned treatment program. Analyses of each outcome will include an assessment of possible differences among clinical centers. Baseline variables that will be used in stratified analyses include gender, HLA risk category and other prognostic characteristics. If differences in baseline characteristics are observed, analyses will be conducted of the effects of the treatments on outcomes adjusting for the potential confounding effects of these baseline characteristics. If only a few such baseline characteristics are identified, analyses will be conducted stratifying for those characteristics. If any more than a few baseline characteristics are identified, because of small sample size, it will be necessary that regression models be employed to adjust the treatment comparison for the confounding effects of those characteristics. A number of subgroup analyses are planned to help identify individuals more likely to benefit from, or to be harmed by, the treatment. In regard to treatment effects, definition of such subgroups will rely on baseline data, not data measured after randomization. Such subgroups might include: gender, gender of the relative with type 1 diabetes, HLA risk group and other factors suspected to be associated with the event. Exploratory data derived through subgroup analyses will serve primarily to generate new hypotheses for subsequent testing, and conclusions drawn from subgroup hypotheses not explicitly stated before data analysis will have less credibility than those from hypotheses stated in the protocol. For safety monitoring, the Data Management Unit also will perform any and all analyses that are appropriate to identify subgroups that may be at significantly increased safety risk. The Kaplan-Meier method will be used to construct survival curves and the logrank statistic used to compare treatment arms with respect to time until the development of autoimmunity or type 1 diabetes.

We therefore aim to randomize 2032 infants with increased genetic risk as defined in the genetic screening section (E). To achieve that number 4516 infants must be screened assuming a frequency of 45% of the genotypes conferring increased risk. The observed prevalence of risk genotypes was 50% among the 471 infants screened for the Pilot-2 trial in Finland. An enrollment scheme for the trial proper is presented in Figure 1. This flow sheet indicates that the trial requires initial access to 5806 pregnancies. This should provide at least 4936 families with consent to participate in the trial before the birth of the child provided that the consent rate is 85%. With an exclusion rate of 8.5% after birth based on the exclusion criteria approximately 4516 infants will be available for genetic screening. The observed exclusion rate in the Pilot-2 trial was 8.6%.

Infants will be recruited over a four-year period and the planned follow-up will be 6 years after the last infant has been accrued for the antibody endpoint and 10 years after the last infant is accrued for the type 1 diabetes end point. Thus, all subjects will have at least 10 years of follow-up.

Figure 1. Enrollment scheme for TRIGR

C. RECRUITMENT

Recruitment is carried out in six major centers in USA, in 18 centers in Canada, in 12 European countries, and three centers in N.S.W., Australia. A list of participating countries and recruitment estimates are presented in Appendix 1. The figures represent an estimate of eligible pregnant women available in each country. The background of these estimates is that the appraisal of the acceptance rate (best scenario 70-80%, average 60%) may vary from country to country, and accordingly the total recruitment figures are a rough estimate. According to the figures given in Appendix 1 about 65% of the participants will be recruited in North America and 35% in Europe + Australia. The recruitment will be continued past the initial 4-year period, if we have not obtained 2,032 newborn infants with increased genetic risk to the series by that time.

To facilitate recruitment and to minimize any possibility of unintentional exposure to CM protein, every attempt is made to identify eligible families before the child is born. Written consent is obtained at this time; the child will participate after birth if he/she meets the inclusion but not the exclusion criteria. Families not identified until just prior to the onset of maternal labor are approached after birth and written consent is obtained at that time.

Mothers with type 1 diabetes are identified during pregnancy via hospitals monitoring pregnant women with type 1 diabetes. Fathers with type 1 diabetes are identified by (i) available history or data already in the medical records of pregnant women, (ii) interviewing women at prenatal maternity clinic visits, and (iii) existing registries of type 1 diabetes in some centers. Pregnant women already having one or more children affected with diabetes are approached through various diabetes clinics. Children with type 1 diabetes are usually followed by pediatricians or pediatric endocrinologists, who are aware of a pregnant mother. The identification of such mothers is arranged through these physicians.

Experience gained in the Pilot-2 study of this project is utilized to optimize the efficacy of the recruitment in the study proper (use of diabetes societies, information in mass media etc.). In that pilot study we also found that weekly staff meetings and continuing recruitment during weekends and vacation periods substantially raises recruitment efficiency. Leaflets, distributed to “candidate” mothers, describing the project can be very helpful.

D. SUBJECT ALLOCATION

Randomization takes place before birth or immediately after the birth of the child. The research assistant or investigator obtains the formula allocation code from the Data Management Unit (DMU) by completing the Randomization Form electronically. Subjects who meet the inclusion and do not meet exclusion criteria are randomized as follows: randomization in each strata will be within four blocks. Subjects will receive either the test formula, casein hydrolysate (Nutramigen™, Mead Johnson Nutritionals), not containing antigenic CM protein, or a CM protein containing control formula which has an addition (20 %) of Nutramigen, whenever breast milk is not available. Any subject requiring supplemental feeding prior to randomization (e.g. infants born at night or on weekends) is given banked breast milk or Nutramigen. The randomization code will be kept by the manufacturer and it will be opened when TRIGR study is completed.

Cord blood is obtained from newborn infants whenever possible or alternatively a heel prick is performed to obtain capillary blood as soon as possible after birth, at the latest at the age of 7 days. The blood sample is forwarded to the continental genotyping center and screening performed for the presence of the genotypes listed below indicating an increased genetic risk. Results are entered into the Central Data Base immediately when available (within 2 weeks after the sampling) and are sent by e-mail from DMU to the national coordinating centers and/or to the local study center in question and to the Study Monitors. Only subjects with these genotypes are included in the nutritional prevention trial; all other subjects are withdrawn from the study at that time; their parents are told that genetic screening suggests that their child does not fall into the increased genetic risk group for type 1 diabetes and they are appropriately thanked for their participation. It is emphasized that their child might still develop diabetes despite not meeting the eligibility criteria.

E. GENETIC SCREENING

The options for genetic screening vary between the extremes of a very high risk population requiring a small sample size (e.g. DQA1*0301-DQB1*0302/DQA1*0501-DQB1*02 heterozygotes), and a lower average risk population with larger sample size (e.g. newborn infants with a FDR but with no additional genetic selection applied). Based on anticipated rates of identification of eligible newborn infants and a feasible enrollment period, we propose to base the selection on the presence of the following genotypes, representing different risk categories:

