and the outcome variables (e.g., the status of the diabetes-associated antibodies). At every time point the single antibody variable will be dichotomized as negative or positive, and a summary variable will be produced (negative if less than two variables are antibody positive and positive if two or more variables are antibody positive). The exposure to formula vs. placebo will be included in the model as an indicator variable. Age at initiation, duration of breast feeding and/or formula use and cumulative formula dose will be included in the model as potential effect modifying and confounding factors. The presence of interactions will be tested and the possible effect of the components considered will be estimated.

Two different statistical methods will be used to analyze the hypothesis that weaning to a casein hydrolysate decreases the occurrence of diabetes-associated antibodies. First, generalized linear models will be fitted to the data (20). Also random effect models will be used (21). These models which represent a general approach to the problem of modeling repeated measurements with fairly general error structures, can allow for missing observations, serial correlations, time-varying covariates, and irregular measurement occasions. Second, for the description of the data, the association of covariates with the risk of an elevated antibody at a given point of time will be assessed using logistic regression models (22). A rather similar statistical approach was used in the DCCT Study (23).

The analyses of the second hypothesis will use the time of diagnosis of manifest type 1 diabetes as the only outcome measure. The dataset will thus be similar to that of a cohort study, and the statistical analyses will be carried out using the proportional hazards regression model (24) including the milk exposure as the risk factor and potential confounding factors a covariates in the model. Also time-dependent covariates can be included to assess the effects of potential modifying factors. The adjusted relative risk of type 1 diabetes between the two groups of milk exposure will be estimated. Also the adjusted incidence of the disease in the two groups can be assessed.

M. INTERIM ANALYSIS

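### Adjustment depends on which baseline differences are observed, no single treatment comparison is fixed as primary, and the randomisation strata are neither named nor tied to an analysis

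*Combined protocol and SAP*

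**What the plan says.** The treatment comparison is described in two places in the protocol, and the allocation in a third.

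**Section B, the analysis paragraph after Table 1**
- Centre: "Analyses of each outcome will include an assessment of possible differences among clinical centers".
- Baseline factors, with no condition attached: "Baseline variables that will be used in stratified analyses include gender, HLA risk category and other prognostic characteristics".
- Adjustment that depends on the data: "If differences in baseline characteristics are observed, analyses will be conducted of the effects of the treatments on outcomes adjusting" for the possible confounding by those characteristics.
- Method that depends on the count: "If only a few such baseline characteristics are identified, analyses will be conducted stratifying for those characteristics". If there are more than a few, "it will be necessary that regression models be employed to adjust the treatment comparison for the confounding effects of those characteristics".
- Time-to-event comparison: Kaplan-Meier curves, with "the logrank statistic used to compare treatment arms with respect to time until the development of autoimmunity or type 1 diabetes". No strata are stated.

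**Section L (Statistical Methods)**
- Time to diabetes is analysed by proportional hazards regression, "including the milk exposure as the risk factor and potential confounding factors a covariates in the model". The confounders are not listed, and no imbalance condition is stated.

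**Section D (Subject Allocation)**
- "randomization in each strata will be within four blocks". The strata are not named there or elsewhere in the supplied text, and neither section B nor section L mentions them.

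**The concern.** In a randomised trial, baseline differences between arms arise by chance. Adjustment is useful because a covariate predicts the outcome, and that can be judged beforehand. A rule that waits to see which variables differ picks covariates on the wrong ground and leaves the form of the main analysis open until the data are seen. Here the rule has no threshold for a difference, no meaning for a few, and no bounded list of variables to examine.

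The unconditional sentence on gender and HLA does not settle the matter. It ends in an open category of other prognostic characteristics and does not say that those analyses are primary. With the log-rank test and the Cox model it makes at least four candidate comparisons:
- an unstratified log-rank test;
- a comparison stratified by gender and HLA;
- an imbalance-triggered adjusted analysis;
- a Cox model with unlisted confounders.

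At stake are the credibility of the headline result, a little power, and agreement between a stratified allocation and its analysis.

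**Working it through.** **1. The plan's own figure.** Inputs from section B and Table 1: 7.6% diabetes by age 10, hazard ratio 0.60, 95% confidence, 80% power, accrual R = 4 years, total duration T = 14 years. Two-sided testing and 1:1 allocation are assumed.

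- λ1 = −ln(1 − 0.076)/10 = 0.007904; λ2 = 0.6 × λ1 = 0.004743
- φ(λ) = λ² / {1 − [e^(−λ(T−R)) − e^(−λT)]/(λR)}, so φ(λ1) = 0.0006907 and φ(λ2) = 0.0004067
- N = 2 × 7.849 × (0.0006907 + 0.0004067)/(0.007904 − 0.004743)² ≈ 1723

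Table 1 column I gives 1735, a difference of 0.7%. With exponential loss reaching 20% at year 10 the same method gives 1963 against 1952 in column II. The further step to 2032 is not reproduced but has no bearing here. The formula has two groups, no strata and no covariates, so fixing an adjusted primary analysis does not change N.

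**2. How prognostic is HLA?** The only denominator below 82 that yields both 15.4% and 18.5% in Table 1 is 65 (10/65 and 12/65), and 18.3% is 15/82. The exact lower 95% limits for 10/65, 12/65 and 15/82 are 7.6%, 9.9% and 10.6%, as section B states. The high-risk group is therefore (15 − 10)/(82 − 65) = 5/17.

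- Hazard ratio, high-risk against the rest: ln(1 − 5/17)/ln(1 − 10/65) = 0.3483/0.1671 = 2.1
- The exact 95% interval for 5/17 is 10% to 56%, and Fisher's p = 0.29. With 10/65 held fixed, 10.3% and 56.0% give hazard ratios from ln(0.897)/ln(0.846) = 0.65 to ln(0.440)/ln(0.846) = 4.9.

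So 2.1 is imprecise. The comparison of 20.7% with 13.0% in section B, ln(0.793)/ln(0.870) = 1.67, is weaker evidence for affected relative. It concerns autoantibodies by age 6, sets a sibling cohort against an extrapolated figure from a separate offspring cohort, and section B itself places 13.0% within the interval around 20.7%.

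**3. Does an imbalance trigger harm the test?** Log-rank trials were simulated at N = 2032 with 20% loss by year 10, 10,000 runs per setting (Monte Carlo error about 0.2 points for the null, 0.4 for power). Assumed, not in the documents: HLA category shares 40/40/20% with relative hazards 1:2:4 or 1:3:9. The triggered test stratifies by HLA only if the baseline chi-square has p < 0.05.

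| HLA hazards, allocation | Null: unadjusted / always stratified / triggered | Power at HR 0.60, same order |
|---|---|---|
| 1:2:4, not balanced on HLA | 5.2 / 5.2 / 5.2% | 81.3 / 81.7 / 81.5% |
| 1:2:4, balanced on HLA | 4.7 / 5.0 / 4.7% | 81.2 / 81.5 / 81.2% |
| 1:3:9, not balanced on HLA | 5.1 / 4.9 / 5.0% | 78.7 / 80.4 / 78.8% |
| 1:3:9, balanced on HLA | 4.6 / 5.2 / 4.6% | 79.7 / 81.2 / 79.7% |

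One fixed trigger on one factor leaves the error near 5%. Always stratifying gains about 0.4 to 1.7 points of power.

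**4. What does free choice cost?** Assumed: 15% high-risk HLA (hazard ratio 2.1) and 30% siblings. Under the null, taking the better of the unadjusted and stratified tests rejects in 5.4% of trials (HLA strata) or 5.7% (HLA and relative strata). Choosing among nine stratifications gives 6.3% to 6.4%. Power for unadjusted against HLA-stratified is 80.8% against 80.9%, or 79.7% against 81.7% if the HLA hazard ratio were 4 (assumed).

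**5. Can the strata be inferred?** Section D places randomisation before or immediately after birth and the HLA result within two weeks of sampling, so HLA is unlikely to be a stratum. Centre is possible but not stated. If the strata were the 77 centres of Appendix 1, sized by its recruitment figures (an assumption), a centre-stratified log-rank has 81.1% power against 81.5% unstratified. Crossing centre with HLA and a two-level relative lowers it to 73.9%.

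**The case against.** The strongest reply is that section B already commits gender and HLA risk category to stratified analyses whatever the balance, that section L puts covariates in the Cox model with no trigger, and that the imbalance rule only adds a further analysis. This largely stands. A reader might infer that known prognostic factors are used only if they happen to be imbalanced. The documents do not support that for gender or HLA. It is nearer the truth for affected relative, where only the gender of the relative appears, as a possible subgroup factor.

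A reader might also infer that the analysis leaves out the randomisation strata. That cannot be shown, because the strata are unnamed. If they are centres, section B does require centre differences to be assessed for each outcome, though it does not make centre a model term. The text supports only that the strata are not named and not linked to an analysis.

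A third inference, that the trigger inflates the type I error, fails in the simulations. The 5.4% to 5.7% arises only if someone takes the better of two results, a rule the plan does not state.

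The reply does not answer the central point: nothing says which of the candidate comparisons is the primary test, and the imbalance rule has no criterion.

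**Conclusion.** The concern holds in a limited form. The plan lets observed baseline differences, and their number, decide whether and how to adjust. It offers several treatment comparisons without naming one as primary, and it does not connect the stratified allocation to the analysis.

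The size is modest: about 0 to 2 points of power, and an error of about 5.4% to 5.7% if the better of two results were taken. These figures rest on assumed HLA shares and hazards, and the HLA hazard ratio of 2.1 comes from 17 children in the high-risk group. How far analysts would in fact choose among models cannot be quantified from the documents. Severity is low to moderate; the main gain is a primary result that cannot be questioned as chosen after the fact.

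**What to change.** - Name the randomisation strata in section D.
- Remove observed imbalance as the trigger for the main comparison.
- State one primary analysis in section L and refer to it from section B. For example: a Cox model with a matching log-rank test, stratified by the randomisation strata, with HLA risk group, affected relative (mother, father, sibling) and sex as fixed baseline covariates whatever the observed balance.
- If the strata are many small centres, group them to region or country. Enter HLA and relative as Cox covariates and do not cross them with the strata, since crossing could lose several points of power (81.5% to 73.9% in the centre example).
- Report the unadjusted log-rank test and any imbalance-based adjustment as sensitivity analyses.

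The cost is wording only. HLA group and affected relative are established for eligibility and sex is known at birth. The sample size does not change. The text should be fixed and dated before the randomisation code is opened, including any opening after an interim analysis under section M.
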